6.4. Assessments at Follow-up Visits

If the patient changes address or is away from home during the follow-up period, the investigator together with the appropriate site personnel can make one or several follow-up visits at the new patient's address. The patient has also the option to perform one or several follow-up visits in another study site or at the Kinshasa coordination (PHLTHA and INRB). The site investigator or the coordinating investigator will take care of the patient. Documents related to these visits will be sent to the original centre so that the data can be entered into the CRF.

6.4.1. At the Additional Visit 9 Weeks after D1

- Haematology: haemoglobin, WBC count and differential, platelet count;
- Biochemistry: same as baseline assessment;
- Physical examination, including vital signs;
- Neurological examination.

6.4.2. At the 3-month Follow-up Visit

- Only at the 6 month visit: Haematology and Biochemistry (same as baseline assessment);
- Physical examination, HAT symptoms since discharge, neurological assessment, including signs and symptoms of HAT;
- Testing for *T.b. gambiense* in blood and lymph for diagnosis of potential relapse;
- CSF sampling and analysis (MSC with INRB kits) only if symptoms suggesting disease progression are present;
- Urine pregnancy test in girls ≥ 12 years of age, to investigate possible exposure *in utero* (see Section 6.5.8. Exposure *in utero*; p 55);
- Additional safety assessments such as ECG, haematology, biochemistry or urine tests may be performed at the discretion of the Investigator. An ECG recording may be required at the M3 visit if the central cardiologist issued an alert at the EOH visit.

6.4.3. At the 6, 12 and 18-month Follow-up Visits

- Physical examination, HAT symptoms since the previous visit, neurological assessment including signs and symptoms of HAT;
- Testing for *T.b. gambiense* in blood and lymph for diagnosis of potential relapse;
- CSF sampling to test for potential relapse, with WBC count and testing for trypanosomes (Fuchs-Rosenthal/Fast Read 102® counting chamber, MSC with INRB kits);
- Additional safety assessments such as ECG, haematology, biochemistry or urine tests may be performed at the discretion of the Investigator.

6.4.4. At Unscheduled Visits

If a relapse is suspected on the basis of physical examination findings or CSF WBC count, at any visit, the patient must attend a return visit within 1 to 3 months, at the discretion of the Investigator.

The patient must also return to the investigational centre if s/he does not feel well, even if there is no apparent relationship with treatment and/or HAT.

The following assessments will be performed:

- Physical examination, HAT symptoms since the last visit, neurological assessment, including signs and symptoms of HAT;
- Investigation of any concomitant condition that may have led to the visit;
- Testing for *T.b. gambiense* in blood and lymph, if indicated;
- CSF sampling (Fuchs-Rosenthal/Fast Read 102[®] counting chamber, MSC with INRB kits): only if symptoms suggesting disease progression are present;
- Additional safety assessments such as ECG, haematology, biochemistry or urine tests may be performed at the discretion of the Investigator.

6.5. Safety Assessments, Definitions and Reporting of Adverse Events

The safety and tolerability of treatment will be assessed through routine monitoring of adverse events (AEs). During the observation period, the study personnel will collect AEs on a daily basis.

The **observation period** will extend from the start of treatment (D1) to hospital discharge, which is planned at D18, but which may take place as early as D13, depending on the patient's status.

In addition, patients will be advised to return to the hospital/investigational centre at any time during the follow-up period if they experience any AEs, in order to undergo additional safety assessments.

Safety data will be reviewed at each meeting of the DSMB.

Safety endpoints will be classified as follows:

- Occurrence of any adverse events grade ≥ 3, including laboratory abnormalities, during the observation period. Adverse events will be graded according to the NCI CTCAE, Version 4.03 (38);
- Occurrence of any adverse events, including laboratory abnormalities, (all grades combined) during the observation period;

- Occurrence of any treatment-related adverse events, including laboratory abnormalities, (grade ≥ 3 and all grades combined) during the observation period and during the follow-up period;
- Occurrence of any serious adverse events, including laboratory abnormalities, during the observation period;
- Occurrence of any serious adverse events, including laboratory abnormalities, between the first intake of the IP and the end of the additional follow-up period (18 months).

6.5.1. Definition of Adverse Event

An AE is defined as any untoward and unintended medical occurrence (sign, symptom or disease), including a clinically significant abnormal laboratory or ECG finding, or worsening of any pre-existing condition during the study, whether or not it is considered to be study related.

Any abnormal laboratory result on haematology, biochemistry or urine analysis must be reported as an AE if it occurs or worsens after the start of the IP, and if the CTCAE grade is > 1, unless it is associated with a previously reported clinical event. Urinary dipsticks are only indicators and are not sufficient to support reporting of an AE. They may orientate the Investigator towards further investigations that, if they show clinically significant abnormalities, may support reporting of an AE.

The Investigator or appropriate study personnel will examine any patient who experiences an AE as soon as possible. The Investigator will do whatever is medically necessary for the patient's safety and well-being. The patient will remain under observation as long as s/he is receiving the IP and up to the last day of the observation period (between D11 and D18), or longer if medically indicated in the opinion of the Investigator. All AEs observed or reported following administration of the IP will be followed until resolved or until the Investigator considers them to be "chronic" or "stable".

All identified AEs will be recorded in the appropriate AE section of the CRF using concise medical terminology, and avoiding vague, ambiguous or colloquial language. SAEs will be reported by telephone, Short Message Service (SMS) or email to Swiss TPH (see Section 6.5.5 Requirements for AE Reporting; p53).

6.5.2. Definition of Serious Adverse Event

An SAE is any AE that:

- results in death;
- is life-threatening;
- requires in-patient hospitalisation or prolongation of existing hospitalisation;

- results in persistent or significant disability/incapacity;
- is a congenital anomaly/birth defect;
- is an important medical event that may not be immediately lifethreatening or result in death or hospitalisation but may jeopardise the patient or may require intervention to prevent one of the other outcomes listed in the definition above.
- In this study, ALAT or ASAT levels higher than 3 x ULN associated with a total bilirubin level higher than 2 x ULN will be considered as SAEs.

SAEs also include any other events defined in the present protocol or by the regulatory authorities in the country in which the event occurs.

For the purposes of the present study, hospitalisation for uncomplicated delivery will not be considered as an SAE.

6.5.3. Collection of Information on Adverse Events

The Investigator is required to report all AEs s/he observes directly, as well as all AEs spontaneously reported by the patient, using concise medical terminology. In addition, during the observation period, i.e. from D1 to D18 (or earlier in the event of early discharge) and at each follow-up visit, the patient will be asked a series of questions, and a targeted physical examination will be performed, to investigate any potential AEs.

6.5.4. Adverse Event Collection Period

The periods for collection of AEs that occur in the context of the study are defined as follows:

- For all non-serious adverse events, the observation period extends from the first intake of fexinidazole on Day 1 until hospital discharge between D12 and D18
- For all serious adverse events, the observation period extends from enrolment of the patient in the study, i.e. after signature of the informed consent form, until the end of follow-up (18 months).

All AEs that occur during the AE collection period defined in the protocol must be recorded in the CRF, whether or not they are considered to be treatment related. In addition, all AEs that occur after the AE collection period, and that the Investigator considers as possibly related to the IP, must also be reported.

6.5.5. Requirements for Adverse Event Reporting

Information on AEs must be assessed by a physician. The Investigator must assess the seriousness of the AE, if necessary with the help of the Coordinating

Investigator and the study monitor. The classification as serious or non-serious will determine the reporting procedure for the event.

All SAEs must be reported immediately, i.e. no later than 24 hours after the Investigator becomes aware of the SAE, to the Swiss TPH clinical study monitor, first by telephone and/or SMS, then by email using the SAE reporting form. This report must include a description of the event, onset date and type, duration, severity, relationship to the IP (with the help of the Coordinating Investigator as needed), outcome and measures taken, as well as any other relevant clinical or laboratory data. Any additional information must be sent on an SAE follow-up form as it becomes available. Follow-up reports should be submitted as soon as possible, and, if possible, within 5 working days after the new information becomes available. A close-out follow-up report must be sent after the final assessment of the case as "recovered", "recovered with sequelae" (chronicity), "death" etc.

SAEs must also be recorded in the AE section of the CRF. It should be noted that the reporting form for SAEs (SAE form) is not the same as the form in the AE section of the CRF. The two forms must be completed in a consistent manner, using the same medical terminology.

All AEs must be recorded in the CRF.

For the purposes of this study, the Coordinating Investigator will be in charge of reporting Suspected Unexpected Serious Adverse Reactions (SUSARs) considered to be related to the IP and SAEs to the Ethical Committees in the countries and other relevant ethical committees. DND*i* will be responsible for reporting SUSARs and SAEs to the regulatory authorities.

6.5.6. Grading of Adverse Event Severity

The severity of the AE will be graded according to NCI CTCAE, version 4.03 (38) adapted for some biological parameters (i.e. haemoglobin, leukocytes, sodium, calcium and creatinin). If the AE is not described in the CTCAE, version 4.03, the Investigator will use the terms "mild", "moderate" or "severe" to describe the maximum severity, as defined below:

Mild does not interfere with the patient's usual activities;

Moderate interferes to some extent with the patient's usual activities;

Severe significantly interferes with the patient's usual activities.

The information concerning AE grading must be recorded in the AE section of the CRF.

It is important to distinguish between the severity and the seriousness of AEs: a severe AE is not necessarily an SAE.

6.5.7. Assessment of Adverse Event Causality

For all AEs, the Investigator is required to assess the possible causal relationship between the IP and the AE, with the help of the Coordinating Investigator as needed, in order to determine whether there is a reasonable possibility that the IP caused or contributed to the AE.

The causal relationship between the IP and the AE is assessed by the Investigator after a detailed analysis of the event in terms of the biological plausibility, taking into account possible unrelated causes, pre-existing medical conditions, concomitant treatments, the temporal relationship between intake of the IP and onset or worsening of the event, and known patterns of response to the IP in general.

The two types of relationships are defined as follows:

- Unrelated: there is no temporal relationship between intake of the IP and the event, and/or there is a plausible alternative explanation.
- Possibly related: any AE that is not considered as unrelated to the IP and/or for which there is no plausible alternative explanation.

The decision to interrupt, resume or permanently discontinue the IP due to an AE will be left to the discretion of the Investigator, except in situations described in Section 8 Withdrawal Criteria, p 56.

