1.2. Clinical Presentation of HAT

There are two successive stages in the clinical course of HAT. In the first stage, called the haemolymphatic stage or stage 1, trypanosomes are present in the blood and lymphatic system. The clinical signs and symptoms are mild and non-specific, including intermittent fever, headache, pruritus and lymphadenopathy. The signs and symptoms are very similar to those of malaria, which explains why patients with stage-1 HAT are often misdiagnosed with malaria. If it is not diagnosed and treated, HAT will progress to the next stage, called the meningoencephalitic stage or stage 2, in which parasites invade the central nervous system. At this stage, patients display the classic neurological signs associated with HAT, including mental confusion, worsening sleep disturbances and, eventually, coma and death (3, 33, 49).

Dividing the patients into two categories is in fact arbitrary, and is based on the differing capacity of the two drugs currently available to cross the blood-brain barrier and reach the cerebrospinal fluid (CSF) and brain (NECT crosses the blood-brain barrier while pentamidine does not), as well as on their toxicity and constraints related to their use, i.e. intramuscular for pentamidine and twice daily intravenous infusion + oral treatment three times daily for NECT. However, the

distinction between stage-1 and stage-2 HAT is not always clear and simple. Indeed, some patients with so-called "early" stage-2 HAT can be treated with pentamidine, however the risk of relapse seems to increase with the number of white blood cells (WBC) in the CSF. Given the risk that patients who relapse will be lost to follow-up, most national HAT control programmes have elected to treat patients with "early" stage-2 HAT systematically with NECT.

The clinical presentation of HAT is identical in children and adults. The progression to stage 2 seems to be more rapid in children, particularly in younger children in whom HAT is generally not diagnosed until it has reached stage 2.

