1.8. Safety and Tolerability in Healthy Volunteers

Fexinidazole has been investigated in three phase-I studies in healthy volunteers of sub-Saharan African origin (15). In all three studies, the subjects were closely monitored, with physical examinations, vital signs, electrocardiogram (ECG) and safety laboratory tests, as well as pharmacokinetic sampling performed before, during and after dosing. A total of 118 subjects were randomised in these studies. Single doses ranged from 100 mg to 3600 mg, and multiple doses from 1200 mg to 3600 mg for a maximum of 14 days.

Administration of fexinidazole in healthy volunteers was safe when given as a single dose or as repeated doses for 14 days. As with all nitroimidazole drugs, fexinidazole primarily affects the central nervous system (CNS) and gastrointestinal system, and can cause headache and/or vomiting or other mild to moderate gastrointestinal symptoms. At the highest dose, two subjects experienced prolonged anxiety with an episode of panic attack, associated with nausea and vomiting. No specific treatment was needed. Both subjects returned to normal within 2 to 3 days after stopping the investigational product (IP).

Fexinidazole is highly metabolized. As expected with this pharmacological class, a marked, transient, quickly reversible increase in liver enzymes was observed in one volunteer just after treatment at the highest dose for 14 days. These abnormalities were not observed in volunteers exposed to fexinidazole for 10 days. Data from these studies also suggest that there is a relationship between the dose used, as well as overall exposure (dose and duration), and the frequency and severity of abnormalities on liver function tests.

Another important laboratory finding was an increase, within the normal range, in plasma creatinine levels in subjects receiving the active treatment. This effect was not dose-dependent and is believed to be related to inhibition of renal tubular creatinine secretion, an effect that has previously been reported with nitroimidazole drugs (21). It is always reversible and is not accompanied by any other abnormalities on kidney function tests.

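### The causality definitions in section 6.5.7 overlap and conflict with the section's own caused-or-contributed standard, so treatment-related events may be understated

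*Protocol*

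**What the plan says.** Section 6.5.7 sets the question as "whether there is a reasonable possibility that the IP caused or contributed to the AE". It tells the investigator to analyse the event in detail, weighing timing, other causes, pre-existing conditions, concomitant treatments and the known response pattern of the drug. It then gives two categories:

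- The label *unrelated* applies when "there is no temporal relationship between intake of the IP and the event, and/or there is a plausible alternative explanation". Either limb can be met alone.
- The remaining label, *possibly related*, is meant as the residual category but carries a second limb of its own: it covers events with no plausible alternative explanation as well as those not classed as unrelated.

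On the drug, section 1.8 says "fexinidazole primarily affects the central nervous system (CNS) and gastrointestinal system, and can cause headache and/or vomiting or other mild to moderate gastrointestinal symptoms". On the disease, section 1.2 describes stage-1 signs as "mild and non-specific, including intermittent fever, headache, pruritus and lymphadenopathy" and gives confusion and disturbed sleep among the stage-2 signs.

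Four things use the label:

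- **Endpoint.** Section 2.2.2 lists treatment-related AEs (grade 3 or higher, and any grade) over the observation period. Section 6.5 lists them over the follow-up period as well.
- **Late reporting.** Section 6.5.4 ends non-serious AE collection at hospital discharge. Of later AEs, it adds that those "that the Investigator considers as possibly related to the IP, must also be reported".
- **SUSARs.** Section 6.5.5 assigns the reporting of SUSARs considered related to the product.
- **Extended follow-up.** Section 6.5.9 continues follow-up beyond a patient's participation for all SAEs and for events judged possibly related.

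Section 6.5.4 also requires every AE in the collection period to be entered in the CRF whatever its causality.

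**The concern.** A plausible alternative does not exclude a contribution from the drug, yet the definition treats it as if it did. The standard and the category can therefore give opposite answers for the same event. In this population the conflict is likely to arise: every child has the disease, and the disease produces symptoms of the kind the drug is known to cause. The trial has a single group, so it has no concurrent arm showing how often headache or CNS events occur without fexinidazole. At stake are one named secondary safety endpoint and the processes that use the same label.

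**Working it through.** **1. The definitions as logic.** Let T mean that the timing fits, and A that a plausible alternative exists. With and/or read in its usual inclusive sense, *unrelated* is (not T) or A, and *possibly related* is (not *unrelated*) or (not A).

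| Timing fits (T) | Alternative exists (A) | Unrelated? | Possibly related? |
|---|---|---|---|
| yes | no | no | yes |
| yes | yes | **yes** | **no** |
| no | no | **yes** | **yes** |
| no | yes | yes | no |

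Row 2 is the conflict with the standard: timing fits, the event may be a known drug effect, a contribution is reasonably possible, and the only label available is *unrelated*. Row 3 is the overlap: both labels apply, so two sites could classify the same event differently, and one choice counts as related an event whose timing does not fit. If a site instead read the and/or in the first definition as a plain *and*, row 2 would no longer be *unrelated*. The wording does not settle which reading applies.

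**2. How readily row 2 arises.** Headache is named both as a stage-1 symptom (1.2) and as a drug effect (1.8). For other CNS effects the overlap is at organ-system level: section 1.8 reports anxiety with panic attack at the highest dose, and section 1.2 lists confusion and sleep disturbance. Vomiting and other gastrointestinal effects are not listed as HAT symptoms. Alternatives for them would have to come from other illness or co-medication, and the documents do not show how often those would be plausible.

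**3. What depends on the label.** Within the collection window a mislabelled event is still in the CRF and can be re-examined. After discharge, a non-serious event labelled *unrelated* need not be reported under 6.5.4, and section 5.8.4 sends other follow-up medical events to the patient's medical file only. To the extent that the section 6.5 version of the endpoint (which includes follow-up) is used, the label decides which late non-serious events must reach the database.

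**4. Size.** The documents state no rate of drug-related events and no misclassification rate, so there is no figure to reproduce. As an illustration only, let p be the true proportion of the 125 children with a drug-related event, and s the share of those children recorded as having none because an alternative was plausible. Ignoring errors in the other direction, the expected recorded rate is p × (1 − s). Both p and s are assumptions.

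| p (children) | s = 25% | s = 50% | s = 75% |
|---|---|---|---|
| 10% (12.5) | 7.5% (9.4) | 5% (6.25) | 2.5% (3.1) |
| 20% (25) | 15% (18.75) | 10% (12.5) | 5% (6.25) |
| 40% (50) | 30% (37.5) | 20% (25) | 10% (12.5) |

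A confidence interval does not repair such an error. With p = 20% and s = 50%, about 12 of 125 are recorded and the exact 95% interval is 5.1% to 16.2%, which excludes 20%. With p = 10% and s = 50%, about 6 of 125 are recorded and the interval is 1.8% to 10.2%, which still includes 10%.

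**The case against.** The strongest reply is that 6.5.7 does not leave the label to the definition alone. It requires a reasoned analysis that includes timing and the known response pattern. A careful investigator who starts from the caused-or-contributed question would call a post-dose headache possibly related. This stands in part: it makes uneven application as likely as a systematic shift. It does not remove the conflict, because when the analysis ends with fitting timing, a known effect and HAT also plausible, the written category is still *unrelated*.

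Several further points limit the consequence:

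- Under 6.5.1 a pre-existing condition is an AE only if it worsens, and HAT signs are recorded at baseline (6.2.3). A stable HAT headache therefore never needs attribution.
- Malaria is tested for and treated if positive, helminth treatment is required, and a recovery period precedes fexinidazole (4.3, 5.8.1, 5.8.2).
- SAEs are reported whatever their causality (6.5.5), and the DSMB reviews SAEs and AEs leading to discontinuation (10.1).
- Children are asked about AEs at each follow-up visit (6.3.1, 6.5.3), so a late event may still be in the source documents.
- Section 1.12 plans a comparison with the adult pivotal study, which has a NECT arm. This gives some context, although it is not a concurrent control in children.

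A reader might infer that treatment-related events will certainly be undercounted, that the number of children reclassified can be stated, or that nothing in the trial could reveal the error. The documents support none of these. Row 3 can push events the other way. No event rate is given, and counting every on-treatment headache or vomiting episode as drug-caused would treat correctly unrelated events as errors. The all-cause counts do not depend on the label.

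**Conclusion.** The point holds as an internal contradiction with a possible effect on safety reporting. On the text the conclusion is firm: the *unrelated* category is wider than the section's own standard allows, and the two categories are not mutually exclusive. For drug-contributed events with fitting timing, literal use can only lower the recorded related rate. For events with no temporal relationship and no alternative, it can raise it. The net effect may be an understatement of the treatment-related endpoint and of late non-serious reports, with possible effects on SUSAR classification and extended follow-up. Its size is unknown, and the illustrated range rests wholly on assumed p and s. All-cause AE counts in the collection period, grade 3 or higher AE counts, SAE counts, the efficacy decision rule and the sample size are untouched.

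**What to change.** Replace the two definitions in section 6.5.7 with exact complements tied to the section's opening question:

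- *Unrelated*: there is no reasonable possibility that the product caused or contributed to the event, because the timing is incompatible or because another cause fully accounts for it.
- *Possibly related*: every other AE.

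Add one sentence saying that the mere existence of another possible cause (HAT, malaria, helminths or co-medication) does not make an event unrelated.

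The cost is a short text change and a training note to sites. The downside is that somewhat more events will be classed as related and more reports will need assessment. No endpoint, analysis or sample-size figure changes.
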